12.5 Demographics and Baseline Characteristics: Descriptive Analyses

Measured outcome variables will be summarized overall and by relevant demographic and baseline variables. Descriptive statistics such as frequencies and relative frequencies will be computed for all categorical variables. Numeric variables will be summarized using simple descriptive statistics such as the mean, standard deviation and range. A variety of graphical techniques will also be used to display data, ex. histograms, boxplots, scatterplots, etc.

12.6 Safety Analysis

Safety and tolerability will be assessed by incidence, severity, and changes from baseline of all relevant parameters including adverse events (AEs) (see **Section 12.8**), laboratory values and vital signs.

Vital sign results (systolic and diastolic blood pressure, pulse, respiration, and temperature) will be summarized descriptively for each scheduled and unscheduled protocol time point. Changes will be calculated relative to the assessments at baseline.

The changes in hematology, chemistry, and other laboratory values will be summarized descriptively for each scheduled and unscheduled protocol assessment time point. Changes will be calculated relative to the values collected at baseline. Data listings of all laboratory data collected during the study will be presented. Laboratory values outside normal limits will be identified in data listings and will include flags for high and low values.

12.7 Efficacy Analysis

12.7.1 Primary Analysis

The primary objective is to evaluate the 6 month PFS survival fraction in patients with newly diagnosed GBM treated with at least 4 priming doses of SurVaxM and standard-of-care adjuvant

temozolomide as compared to historical control. PFS is defined as the time from date of diagnosis to the date of first observed disease progression or death due to any cause. Patients who are alive and disease free at the last study assessment will be treated as censored.

Historical Control: Patients in this population defined by the eligibility criteria receive standard-of-care which consists of concurrent temozolomide and radiation followed by adjuvant temozolomide. Based on provided historical information, the 6 month PFS survival fraction is assumed to be 0.55. We hypothesize that treatment with SurVaxM and adjuvant temozolomide will increase the 6 month PFS survival fraction to 0.70. Therefore the PFS survival fraction will be measured after all patients have been followed for 6 months.

The 6 month PFS survival fraction is estimated as standard binomial proportion. An exact one-sided binomial test will be used to test our primary hypothisis. The nominal significance level to be used for this test is 0.10. In addition, a Kaplan-Meier curve for PFS will be used calculated to generate summary descriptive statistics, e.g. median PFS.

Secondary Analyses

The estimated distributions of overall survival (OS), defined as the time from date of diagnosis to death due to any cause, will be obtained using the Kaplan-Meier method. Estimates of quantities such as median survival will be obtained. Corresponding confidence intervals will be computed. It is assumed *a priori* that any drop out times will be non-informative in terms of the censoring mechanism. Groups defined by levels of categorical or dichotomized numeric demographic/baseline variables will be compared in regards to time-to-event distributions using the log-rank test. Cox proportional hazards model regression will be utilized for multivariate analyses.

A summary of anticancer therapies received following the discontinuation of protocol therapy will be provided. Such therapies will be classified as chemotherapy, biological therapy, radiation, surgery, or other.

Both objective tumor response rate (applicable only for patients with evaluable disease at study entry, as defined per RANO criteria) and toxicity rate (Grade 3 or Grade 4 toxicities, according to National Cancer Institute Common Toxicity Criteria for Adverse Events (NCI CTCAEs) Version 4) will be estimated using simple relative frequencies. The corresponding 95% confidence intervals for the estimated probabilities will be computed using the method proposed in Clopper and Pearson, 1934 ⁽⁴³⁾. The relationship between binary outcomes and collected demographic and baseline variables will be statistically assessed using logistic regression in an exploratory fashion. Maximum likelihood estimation will be utilized in the model fitting procedures as implemented by SAS PROC LOGISTIC. Wald tests of the model effects will be performed to assess statistical significance; see SAS documentation for details. See Hosmer and Lemeshow, 2000 ⁽⁴⁴⁾ for a discussion of such techniques. Alternative parametric models will be considered if model fit is found to be inadequate.

Objectives based on continuous outcomes such as immune response measured over time will be address in a similar fashion. A series of exploratory analyses will initially take place including individual subject-level profile plots and overall mean plots used to examining the mean structure. Formal statistical examination of longitudinal patterns will be done through the use of

a mixed model. Restricted maximum likelihood estimation will be utilized in the model fitting procedures as implemented by SAS PROC MIXED (version 9.2). Once the model is fit, specific linear contrasts based on the estimated model parameters will be constructed and used to test hypotheses concerning between time point comparisons. We acknowledge the possibility of informative missingness, that is, the probability of a particular observation being missing may be related to the health of the subject, and therefore analyses will be interpreted with caution.

All tests will be two-sided and tested at a 0.05 nominal significance level. Standard diagnostic plots will be used to assess model fit and transformations of variables may be considered in order to meet statistical assumptions.

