12.1.1 Missing Data

The amount and nature of missing data will be characterized and no method of imputation will be used for missing data. A summary of missing data will be provided according to the number of subjects, the time points where the data are missing, and clinical center. For each clinical center, the number and percent of subjects with no missing data will be presented in tabular form

All analyses will be performed using the SAS® statistical software system.

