12.4 Sample Size Determination

The primary endpoint will be the 6 month PFS survival fraction. Let π represent the 6 month PFS survival fraction. A true rate of the 6 month PFS survival fraction greater than π_0 =0.55 is considered acceptable and evidence such that we will the treatment worthy of further study. The null and alternative hypotheses to be tested are H_0 : π = π_0 versus H_a : π > π_0 . We hypothesize that patients treated with SurVaxM and adjuvant temozolomide will have a 6 month PFS survival fraction of 0.70 or larger. The sample size calculation is based on testing the hypotheses concerning the proportion of the population with a response to the treatment: H_0 : π = π_0 versus H_a : π > π_0 . For our calculations π_0 =0.55, α =0.10, 1- β =0.80. Based on an exact one-sided test the sample size calculation yields n=50 patients.

Subjects will be accrued to the study on a first-come basis. The projected accrual is approximately 2 subjects per month, and therefore recruitment is expected to be complete at 25 months following the study starting point. Subjects will be followed to determine time to tumor progression (PFS) and until death to determine overall survival (OS).

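### PFS6 is tested as a binomial proportion, but the plan gives no yes/no status to an evaluable patient last seen progression-free before month 6

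*Combined protocol and SAP*

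**What the plan says.** Section 12.7.1 defines the estimator: "The 6 month PFS survival fraction is estimated as standard binomial proportion". The test follows: "An exact one-sided binomial test will be used to test our primary hypothisis", and "The nominal significance level to be used for this test is 0.10". The paragraph that defines PFS as a time from diagnosis also says: "Patients who are alive and disease free at the last study assessment will be treated as censored". Section 12.1.1 adds that "no method of imputation will be used for missing data". The Kaplan-Meier curve in 12.7.1 is for descriptive summaries only.

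Other sections bear on how many patients could lack a month-6 status:

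- Sections 12.3 and 12.7.1 require 6 months of follow-up for all patients before the endpoint is measured.
- Section 9.2.1 scores non-return as progression only when death or a deteriorating condition is the cause.
- Section 6.3 has patients who start another anti-cancer therapy stop the vaccine and be followed for survival. Section 8.1.4 does the same for anyone who stops study treatment, by visit or phone every 12 weeks. The survival follow-up column of Table 3 has no MRI.
- Section 12.9 makes patients unevaluable, and replaces them, if they miss any of the four priming doses or withdraw consent, with no time limit on the withdrawal. Section 12.1 refers to withdrawal before the priming injections.

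**The concern.** A binomial test needs a yes or no for every patient in its denominator and has no place for a censored observation. For a patient last assessed progression-free before month 6, the plan offers only censoring without imputation, and neither yields a yes or a no. The literal result is a complete-case analysis.

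This is the trial's only primary hypothesis test, in a single-arm, open-label study. If the rule is left open, it may be chosen once the data are known, and a few patients can move the count across the threshold. If patients who are doing badly are more likely to lack a month-6 assessment, dropping them raises the observed PFS6, and counting them as progression-free raises it further. Section 12.7.1 itself concedes, for the longitudinal outcomes, that missingness may depend on the patient's health.

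**Working it through.** **Inputs.** From Section 12.4: "For our calculations π_0 =0.55, α =0.10, 1- β =0.80". From Section 12.7.1: "We hypothesize that treatment with SurVaxM and adjuvant temozolomide will increase the 6 month PFS survival fraction to 0.70". The planned size: "Based on an exact one-sided test the sample size calculation yields n=50 patients". The number unknown, m, and the share f of unknowns who are true failures are assumptions, because the documents give neither. The range used is m = 0 to 5 of 50.

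**The plan's own figure.** The critical value r is the smallest with P(X ≥ r | n = 50, p = 0.55) ≤ 0.10.

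- r = 32 gives 0.1273, which is too large.
- r = 33 gives 0.0765, with power P(X ≥ 33 | 50, 0.70) = 0.782.

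The smallest n with power of at least 0.80 is 49 (r = 32, alpha 0.0948, power 0.810). The stated n = 50 is reproduced closely.

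**Unknowns dropped, loss unrelated to outcome.** The critical value is found afresh for n = 50 − m, at p = 0.55.

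| m | n | r | type I error |
|---|---|---|---|
| 1 | 49 | 32 | 0.095 |
| 2 | 48 | 32 | 0.068 |
| 3 | 47 | 31 | 0.085 |
| 4 | 46 | 31 | 0.060 |
| 5 | 45 | 30 | 0.076 |

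All are at or below 0.10.

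**Unknowns dropped, loss related to outcome.** With u = m/50, the success rate among patients with known status is p' = (0.55 − u(1 − f)) / (1 − u).

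- m = 5, f = 0.75: p' = (0.55 − 0.025)/0.90 = 0.5833; P(X ≥ 30 | 45, p') = 0.163.
- m = 5, f = 1: p' = 0.55/0.90 = 0.6111; the tail is 0.273.
- m = 2, f = 0.75: p' = 0.54/0.96 = 0.5625; P(X ≥ 32 | 48, p') = 0.094.
- m = 2, f = 1: p' = 0.55/0.96 = 0.5729; the tail is 0.121.

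A milder case lets each patient be unknown with probability u and makes true failures twice as likely as true successes to be unknown. The error is then 0.098 at u = 5%, 0.101 at 6% and 0.120 at 10%.

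**Unknowns counted as successes, loss unrelated to outcome.** With m fixed, the error is P(X ≥ 33 − m | 50 − m, 0.55): 0.095 (m = 1), 0.117 (2), 0.142 (3), 0.172 (4), 0.206 (5). If instead every unknown is a true failure, the apparent rate is 0.55 + u: 0.59 for m = 2 gives P(X ≥ 33 | 50) = 0.195, and 0.65 for m = 5 gives 0.506.

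**Unknowns counted as failures, loss unrelated to outcome.** The error is P(X ≥ 33 | 50 − m, 0.55), and power uses 0.70 in its place.

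| m | type I error | power at 0.70 |
|---|---|---|
| 0 | 0.0765 | 0.782 |
| 1 | 0.054 | 0.717 |
| 2 | 0.037 | 0.642 |
| 3 | 0.024 | 0.559 |
| 5 | 0.009 | 0.380 |

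Under this rule the apparent success rate cannot exceed the true one, so with 50 evaluable patients and r = 33 the error cannot exceed 0.0765, whatever the pattern of loss.

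**The case against.** The strongest reply is that the censoring sentence belongs to the time-to-event definition just before it and serves the Kaplan-Meier curve. A patient followed past month 6 without progression is censored on the curve and a success in the proportion, with no conflict. That is right for such patients. It leaves open those whose last clean assessment falls before month 6.

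A second reply is that unknowns should be few. Taking surgery as the diagnosis date (an assumption), Sections 4.1 and 6.1 put the fourth priming dose at 4 + 6 + 1 + 6 = 17 to 4 + 6 + 4 + 6 = 20 weeks. That leaves about 6 to 9 of some 26 weeks in which an evaluable patient can be lost. Decline-linked non-return already counts as progression, and the analysis waits for 6 months of follow-up. This stands as a reason to expect small numbers. It does not reduce them to zero: survival follow-up without MRI satisfies the follow-up requirement yet leaves progression status unknown, and unexplained loss is not covered by Section 9.2.1.

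A reader might also infer that the plan forces unknowns to be dropped or counted as successes, and so necessarily inflates the type I error. The documents do not support that. Counting such a patient as a failure is a definition of response that the no-imputation rule does not clearly exclude, and Section 9.2.1 already does this for some non-returns. Dropping does not inflate the error unless loss is informative.

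**Conclusion.** The gap is real: the outcome in the primary test is undefined for an evaluable patient without a month-6 status. The consequence is conditional. Dropping unknowns breaches 0.10 only under informative loss that escapes the deterioration rule; 5 of 50 unknown with 75% to 100% true failures, giving 0.16 to 0.27, is an assumed adverse case, not a forecast. Counting unknowns as successes is the more fragile choice, since 2 of 50 suffice even when loss is unrelated to outcome. The sample size calculation is not at fault. The wording should be settled before the analysis, because the answer should not depend on a choice made with the data in view.

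**What to change.** In Section 12.7.1:

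- Count as a PFS6 success only an evaluable patient documented progression-free at or after 6 months from diagnosis. Count every other evaluable patient as a failure and keep all of them in the denominator.
- Confine the censoring sentence to the Kaplan-Meier curve, and report the Kaplan-Meier 6-month estimate as a sensitivity analysis.
- Because disease assessments fall every 8 weeks (± 4 weeks), say explicitly how the rule applies to a patient whose last clean scan precedes month 6 and whose progression is first seen after it. Section 12.3 would give that patient a PFS above 6 months, while the rule above, read strictly, makes the patient a failure.

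Reconcile Sections 12.1 and 12.9 so that withdrawal of consent after the four priming doses does not remove a patient from the denominator.

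The change is to wording only, but it is not free. The PFS6 estimate becomes less favourable, and if unknowns are unrelated to outcome, power at 0.70 falls from 0.78 to 0.72 with 1 unknown, 0.64 with 2 and 0.38 with 5. Obtaining a month-6 disease assessment wherever possible, including after treatment stops, would limit that loss.

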12 STATISTICAL METHODOLOGY

12.1 Study Design

This is a multi-center, open-label; prospective one-arm phase II clinical trial evaluating the safety and efficacy of SurVaxM and adjuvant temozolomide in adult patients with newly diagnosed GBM. The statistical design is based on an assessment of the efficacy of the study treatment for patients as compared to an external standard, i.e., historical control. All enrolled patients will receive the study treatment and initiation of the treatment should take place as soon as possible following study enrollment. A total of up to 65 patients will be enrolled to meet our target of at least 50 evaluable patients. An evaluable subject is defined as a subject who meets eligibility requirements and who completes the initial four priming doses of the vaccine. If a patient signs an Informed Consent and does not receive all four priming injections or, the patient withdraws their consent before receiving the priming injections, the patient will be classified as unevaluable and will be replaced. Analyses will be performed with a focus on estimation of specific clinically important parameters for use in the planning of larger subsequent comparative trials designed to fully assess efficacy and safety.

All analyses will be performed using the SAS® statistical software system.

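### Survival comparisons split numeric baseline variables at unstated cut-points; continuous Cox terms would usually use 50 patients better, at the price of assuming a functional form

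*Combined protocol and SAP*

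**What the plan says.** Section 12.7.1 of the combined protocol and SAP, under Secondary Analyses, uses the log-rank test to compare the time-to-event experience of "Groups defined by levels of categorical or dichotomized numeric demographic/baseline variables". Neither that section nor the rest of Section 12 names the variables to be split, gives cut-points, or gives a rule for choosing them.

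The next sentence plans Cox regression for multivariate analyses. It does not say whether numeric covariates enter that model as continuous or as groups, and it does not list a one-variable Cox model.

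Later in the same part, tests are set at a two-sided nominal 0.05. Diagnostic plots are planned and transformations of variables are allowed. For binary outcomes, baseline variables are related to outcome by exploratory logistic regression, with no mention of dichotomising.

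The primary analysis is separate and uses no baseline covariate: "An exact one-sided binomial test will be used to test our primary hypothisis".

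**The concern.** Splitting a numeric variable treats all patients on one side of the cut as alike and discards the ordering within each side. The trial is sized at 50 evaluable patients and these comparisons have no power calculation, so there is little information to spare. The plan already contains a model that can use the full scale, which makes the split avoidable.

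The second issue is the open cut-point. A nominal 0.05 test keeps its error rate if the cut is fixed in advance, but not if the cut is chosen because it separates the curves best. Nothing in Section 12 rules out that choice.

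At stake is whether a prognostic relationship in this small cohort is missed, or reported when it is not there.

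**Working it through.** **The plan's own figure.** Section 12.4 assumes 0.55 under the null and 0.70 under the alternative, with "α =0.10, 1- β =0.80", and reports: "Based on an exact one-sided test the sample size calculation yields n=50 patients". For the exact one-sided test at n=50, the smallest rejection count with type I error at or below 0.10 is 33. This gives an exact alpha of 0.0765 and power of 0.782. At n=49 the count is 32, with alpha 0.0948 and power 0.810. The stated size is therefore reproduced to within one patient and two points of power. Nothing below changes it. The plan states no power or event count for the log-rank comparisons, so there is no figure of its own to reproduce for them.

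**Inputs.** From the documents: 50 evaluable patients; two-sided 0.05; follow-up of at least 12 months after the last enrolment (Section 4.2). Assumed, because the documents are silent: a standard normal covariate, a log-linear hazard, 25 to 45 deaths among 50 patients, and hazard ratios of 1.3 to 2.0 per SD.

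**Information kept by a split.** For a normal covariate cut at c, with a proportion q below the cut, relative efficiency is φ(c)²/[q(1−q)].

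- Median: 0.3989²/0.25 = 0.637, so 50 × 0.637 ≈ 32 patients' worth.
- 25/75: 0.539, or about 27 patients.
- 20/80: 0.490, or about 24 patients.

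Karnofsky status is coarser. Eligibility requires at least 70 and the scale moves in tens, so at most four levels enter. Under a linear effect, the share kept is the between-group variance divided by the total variance. Scoring the levels 0 to 3 and cutting in the middle:

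- Equal frequencies: 1.00/1.25 = 0.80.
- An assumed 10/30/40/20% distribution: 0.602/0.81 = 0.74.

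**Power.** The approximation is Φ(√(D × efficiency) × ln HR − 1.96), where D is the number of deaths. For D=35 and HR 1.5:

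- Continuous: Φ(5.916 × 0.405 − 1.96) = 0.67.
- Median split: Φ(4.720 × 0.405 − 1.96) = 0.48.

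Simulated score tests with n=50 and 20,000 replicates per setting gave:

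| HR per SD | Deaths | Continuous | Median split | Loss (points) |
|---|---|---|---|---|
| 1.3 | 35 | 0.33 | 0.22 | 11 |
| 1.5 | 25 | 0.52 | 0.34 | 17 |
| 1.5 | 35 | 0.63 | 0.45 | 18 |
| 1.5 | 45 | 0.73 | 0.53 | 20 |
| 2.0 | 25 | 0.91 | 0.71 | 20 |
| 2.0 | 45 | 0.99 | 0.90 | 8 |

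A separate run at HR 1.57 per SD with about 79% events gave 0.75 against 0.55, a loss of 20 points.

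**False positives.** With no true effect, the continuous test and the fixed median split both reject at about 0.05. Taking the best of seven cuts (20% to 80% in steps of 10%) rejects at 0.21, 0.21 and 0.23 with 25, 35 and 45 deaths.

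**Where the order reverses.** Suppose the true effect is a step at the median, with log hazard ±ln 1.5 on either side, that is, a hazard ratio of 1.5² = 2.25 between halves. With 35 deaths, power is 0.47 for the continuous term and 0.56 for the median split.

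**The case against.** The strongest reply is that this is a preference about unpowered secondary comparisons, and that much of the remedy is already in the plan. The Cox sentence may well mean continuous covariates, and diagnostics and transformations are provided for. Groups also give readable Kaplan-Meier curves. That stands in part. What remains is that the covariate form in the Cox model is unstated, no one-variable Cox model is listed, and the one-variable comparison that is listed uses a split with an open cut-point.

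Some stronger readings are tempting but are not supported:

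- *Keeping variables continuous costs nothing.* It needs no extra data, but it assumes a functional form, and the step example shows the split can win.
- *The plan will split age, Karnofsky status and immune levels.* It names no variables. Immune response over time is assigned to a mixed model.
- *Cut-points will be chosen from the data.* The plan does not say so. The 0.22 shows what that choice would do; it is not a forecast.
- *Planning of the next trial is compromised.* Section 12.1 speaks generally of estimating clinically important parameters and mentions no prognostic factors. The stated objectives on predictors concern immune and tumour response, not survival.

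**Conclusion.** The point holds as a minor, inexpensive improvement. If effects are roughly log-linear and the covariate roughly normal, a median split discards about 36% of the information. At hazard ratios of 1.5 to 1.57 per SD this costs about 17 to 20 points of power with 50 patients; the table shows smaller losses where the effect is weak or power is already near its ceiling. A coarse scale such as Karnofsky status loses roughly 20 to 26% of the information under the two distributions shown.

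The open cut-point is the firmer reason to act, because the rise from 0.05 to about 0.22 under best-of-seven selection is calculated with no true effect and so does not depend on log-linearity. It arises only if cuts are chosen after seeing the data.

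A reader should not infer that the trial's main conclusion is at risk: the test of 6-month PFS and its sample size are unaffected.

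**What to change.** In the Secondary Analyses text of Section 12.7.1:

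1. State that each numeric baseline variable is tested as a continuous term in a univariable Cox model and enters the multivariable Cox model as continuous.
2. Add a linearity check, using the diagnostics and transformations the plan already allows.
3. Keep groups for Kaplan-Meier display only, at cut-points fixed before analysis (for example, the median). Keep the log-rank test for variables that are genuinely categorical.

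The cost is SAP wording. No patients, visits, data or alpha are needed. The small downside is some loss of power where the true effect is a threshold.
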